12.6.2.3 Supplementary Analysis

In case of any uncorrected nicotine concentration at T_0 [uC₀] greater than 25% of their uncorrected maximum value, a supplementary analysis of the endpoints will be performed similarly to the main analysis, whereby data of these subjects for this specific study day will be excluded from the analysis.

An analysis of covariance (ANCOVA) will be conducted by product use. The PK parameters will be transformed in the natural logarithmic scale. The model will include terms for sequence, period and a PD parameters mentioned in the objective 4. The results of this analysis will be presented by product in terms of:

- The percentage of variance explained by the PD parameter
- The standardized effect of the PD parameter, defined as the mean effect divided by the square root of its variance.

Another analysis of covariance (ANCOVA) will be conducted similarly at the exception that it will be performed overall using mixed effects ANCOVA where the model will include additionally the subject as a categorical random effect to model the within subject correlations.

A multivariate analysis will be performed to analyze the joint effect of nicotine concentration, PH and moisture. The PK parameters will be transformed in the natural logarithmic scale. The model will include be adjusted for product use, sequence, period, and covariates encoded as low and high for nicotine concentration, PH level and moisture percentage. The results of this analysis will be presented for all products. The output will contain regression coefficients and their confidence intervals for factors of interests. Further details will be provided in the SAP.

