7.3 Inferential Analysis

An analysis of covariance (ANCOVA) will be conducted by product use. The PK parameters (C_{max} , T_{max} , AUC_{infinity}, as applicable) will be transformed (except for the T_{max}) in the natural logarithmic scale. The model will include terms for sequence, period and the PD parameters mentioned in the Objective 4. The effect of VAS score will be analyzed in different models with:

- VAS-liking "in the moment" averaged over the product use period (from T1 to T6)
- VAS-liking "in the moment" averaged during the sequence period (T1 to T9)

Statistical Analysis Plan Number CA36095

- VAS product satisfaction "in the moment" during the sequence's period (from T1 to T11)
- VAS-craving averaged during the sequence's period (from T1 to T11)
- PES
- Sensory questionnaire

The results of this analysis will be presented by product in terms of:

- The percentage of variance explained by the PD parameter
- The standardized effect of the PD parameter, defined as the mean effect divided by the square root of its variance.

The ANCOVA analysis will be performed using the following SAS code:

PROC MIXED data=<> method=type3;

By product;

class sequence period;

model log(PK parameter) = sequence period score/ddfm=KR solution;

run;

A multivariate analysis to analyze the marginal effect of nicotine concentration, pH and moisture of NP 1.0 products will be performed. This analysis will be done using only NP 1.0 data. The PK parameters will be transformed in the natural logarithmic scale. The model will include covariates encoded as low and high for nicotine concentration (3.6 mg = LOW and 8.4 mg = HIGH), PH level (8.0 = LOW and 9.0 = HIGH) and moisture percentage (15% = LOW and 30% = HIGH).

The results of this analysis will be presented by product in terms of:

- The percentage of variance explained by the covariates (nicotine concentration, pH level and moisture)
- The standardized effect of the covariates (nicotine concentration, pH level and moisture) defined as the mean effect divided by the square root of its variance.

The multivariate analysis will be performed using the following SAS code:

PROC MIXED data=<> method=type3;

By product;

Class Nicotine concentration PH Moisture

model log(PK parameter) = Nicotine_concentration PH Moisture/ddfm=KR solution; run;

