Another ANCOVA will be conducted similarly to the above with the exception that it will be performed overall using mixed effects ANCOVA where the model will include, in addition, the subject as a categorical random effect to model the within subject correlations.

The ANCOVA analysis will be performed using the following SAS code:

PROC MIXED data=< > method=type3; By product sex; class subject sequence period; model log(PK parameter) = sequence period score/ddfm=KR solution; random subject; run;

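### SAP 7.3 codes the nicotine/pH/moisture model by product and the overall PK-PD ANCOVA by product and sex, so neither planned output is produced as written

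*SAP*

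**What the plan says.** **Factor model.** Protocol 12.6.2.3 plans a joint analysis of nicotine content, pH and moisture, "adjusted for product use, sequence, period, and covariates encoded as low and high for nicotine concentration, PH level and moisture percentage". Results are to cover all products and give regression coefficients with confidence intervals. SAP 7.3 restates the aim as marginal effects and restricts the data: "This analysis will be done using only NP 1.0 data". It then says "The results of this analysis will be presented by product in terms of" variance explained and standardized effect. The code carries `By product` and the model line is "model log(PK parameter) = Nicotine_concentration PH Moisture/ddfm=KR solution; run".

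**Second PK-PD ANCOVA.** Protocol 12.6.2.3 says "it will be performed overall using mixed effects ANCOVA where the model will include additionally the subject as a categorical random effect". The SAP text agrees: "performed overall using mixed effects ANCOVA where the model will include, in addition, the subject as a categorical random effect". The SAP code reads "By product sex; class subject sequence period; model log(PK parameter) = sequence period score/ddfm=KR solution; random subject; run".

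**First PK-PD ANCOVA.** SAP 7.3 says "An analysis of covariance (ANCOVA) will be conducted by product use". Its code is by product, which matches both its own text and the protocol.

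**Declared changes.** SAP section 9 lists added VAS AUCs and a spirometry clarification, and states that everything else agrees with the protocol.

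**The concern.** A BY statement splits the data before the model is fitted. Splitting by product removes the only variation that the factor model could use, because nicotine content, pH and moisture differ between products and never within one. For the second ANCOVA, splitting by product removes the repeated records that would give a random subject effect something to estimate, and it removes the pooling that makes the analysis overall.

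A programmer who follows the SAP obtains no factor estimates and no pooled PK-PD slope. One who notices the problem must choose a replacement model after the SAP is final, possibly with data in hand. Pre-specification is meant to prevent that choice.

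**Working it through.** The plan gives no numerical figure for these analyses, so the check is whether each model can be estimated.

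**Inputs**
- 24 subjects, six products, six sequences (SAP 3.1). Each subject uses each product once. I assume four subjects per sequence and complete data.
- Product attributes (SAP Table 5.1), with the low/high coding of SAP 7.3:

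| Variant | Nicotine | pH | Moisture |
|---|---|---|---|
| NP-1 | high (8.4 mg) | low (8.0) | high (30) |
| NP-2 | high (8.4 mg) | high (9.0) | high (30) |
| NP-3 | low (3.6 mg) | low (8.0) | low (15) |
| NP-4 | low (3.6 mg) | low (8.0) | high (30) |

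- Sex quota of at least 25% (SAP 3.2), so the smaller sex may number 0.25 × 24 = 6.
- Periods: six in SAP 3.1 and protocol 12.9.1, three in protocol 4.1. Both are carried through.

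**Factor model, by product as coded.** Each run has 24 records and one level of every factor. The rank of [intercept, nicotine, pH, moisture] is 1, so 0 of 3 effects are estimable.

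**Factor model, pooled over NP-1 to NP-4.** There are 96 records and the rank is 4, so 3 of 3 effects are estimable. Solving the four cell means gives:
- nicotine = NP-1 minus NP-4
- pH = NP-2 minus NP-1
- moisture = NP-4 minus NP-3

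A product term alone has rank 4, and product plus the three factors also has rank 4. If the protocol's adjustment for product use means a product term, it is fully aliased with the factors.

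**Second ANCOVA, by product.** Each product has 24 records from 24 subjects. The subject columns alone have rank 24, so subject variance is confounded with residual error. Splitting by sex as well gives 6 × 2 = 12 fits per PK-PD pair.

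Objective 4 lists these pairs: liking 2 averages × 3 PK parameters = 6, satisfaction 3, craving 3, PES scales 7, sensory items 9, in total 28. That makes 28 × 12 = 336 fits in place of 28. Without the three single-item PES scales it is 25 × 12 = 300 in place of 25.

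**Product-by-sex cells.** Leaving the random subject term aside, a cell of n subjects spread over k sequences has n − k − 1 residual df, because period is determined by sequence within one product. For n = 6:

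| Sequences covered | Residual df |
|---|---|
| 2 | 3 |
| 3 | 2 |
| 4 | 1 |
| 5 | 0 |
| 6 | slope not estimable |

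With all six sequences covered, 12 subjects give 12 − 7 = 5 df and 18 give 18 − 7 = 11. The actual sex-by-sequence split is not in the documents.

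**Corrected and unaffected models.** Subject is counted as fixed to show the within-subject df; Kenward-Roger df with random subject will differ.

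| Model | Records | Residual df, six periods | Residual df, three periods |
|---|---|---|---|
| Pooled factor model | 96 | 96 − (24 + 5 + 3) = 64 | 96 − (24 + 2 + 3) = 67 |
| Overall ANCOVA | 144 | 144 − (24 + 5 + 1) = 114 | 144 − (24 + 2 + 1) = 117 |
| Overall ANCOVA plus product | 144 | 114 − 5 = 109 | 117 − 5 = 112 |
| By-product ANCOVA (no subject term) | 24 | 24 − (6 + 1) = 17 | 17 |

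**The case against.** The strongest reply is that little is lost. The study is exploratory with no hypothesis (SAP section 2), the by-product ANCOVA still serves objective 4, and SAP Table 6.2 already reports, with 95% confidence intervals, the three product contrasts that equal the factor effects apart from sign. This is correct and limits the weight of the point, but two specified outputs still cannot be delivered from the SAP as written.

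For the second ANCOVA, the SAP prose states the right analysis and only the code contradicts it. That is fair: this half is a conflict between code and text. Protocol 12.1.1 asks for sex-stratified and unstratified analyses, which may explain BY sex. It does not explain BY product. The factor model has no such defence, since its prose also asks for results by product.

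Four further qualifications stand:
- The protocol's factor model names no subject term. Adding one is my recommendation, because each subject contributes four records once the data are pooled; it is not a departure from the protocol.
- Protocol 12.9.4 already calls for 95% confidence intervals wherever inference is made. The SAP code and its list of outputs omit them but do not cancel that requirement.
- The small cell df describe the minimum quota, not an expected split.
- In the by-product ANCOVA the period term is redundant given sequence. The score slope is unaffected.

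**Conclusion.** The concern holds and should be fixed. As coded, the factor model estimates none of its three effects, and the overall ANCOVA gives 12 product-by-sex slopes per PK-PD pair instead of one pooled slope, with a random subject term that cannot be separated from residual error. The factor model also drops the protocol's sequence and period adjustment. Section 9 is therefore wrong to declare alignment.

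The rank results for the factor model follow directly from the product table. The one-record-per-subject result follows from each product being used once. Neither depends on the number of periods. The df figures assume four subjects per sequence and no missing data. The main PK ANOVA and the by-product ANCOVA are unaffected, so the loss is confined to supplementary exploratory outputs.

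**What to change.** 1. **Factor model.** Delete `By product` and the sentence asking for results by product. Pool NP-1 to NP-4 and fit the three low/high factors with sequence, period and random subject (or the main model's within-subject covariance). Include no product term, and clarify what the protocol's adjustment for product use means. Report coefficients with 95% confidence intervals. State that the effects assume no interaction: pH varies only at 8.4 mg and moisture 30, and moisture only at 3.6 mg and pH 8.0.
2. **Overall ANCOVA.** Delete `By product sex`. Fit all six products together with sequence, period, score and random subject, as both texts describe. Describe the slope as mixing between-subject, within-subject and between-product information. Add product only in a labelled sensitivity analysis, because it removes between-product differences and so changes what the slope means. Run any sex-stratified version in addition, by sex only.
3. **By-product ANCOVA.** Leave it as it is.
4. **Section 9.** Align code with text and list any departure from protocol 12.6.2.3 that remains.

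The cost is SAP wording and a few lines of code. No new data are needed.

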6 INVESTIGATIONAL PRODUCTS

6.1 Description of Investigational Products

NP 1.0, Velo-NP and Zyn-NP will be provided by the Sponsor.

The distribution and return of investigational products will be controlled by qualified and appropriately trained investigational site staff.

Name	Nicotine per pouch	рН	Moisture	Flavor
NP-1	8.4 mg	8.0	30	Cool mint
NP-2	8.4 mg	9.0	30	Cool mint
NP-3	3.6 mg	8.0	15	Cool mint
NP-4	3.6 mg	8.0	30	Cool mint

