9. SUMMARY OF CHANGES FROM PROTOCOL-PLANNED ANALYSIS

In section 7.2 AUCs related to T1 to T11 for VAS craving assessment, VAS liking assessment and VAS satisfaction assessment have been added to the descriptive statistics.

In section 8.12, it is specified that the investigator will define ranges to determine normal or abnormal Spirometry results.

All other analyses described in this SAP are aligned with those analyses described in the protocol.

Statistical Analysis Plan Number CA36095

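### The nicotine/pH/moisture model in SAP 7.3 omits the protocol's sequence and period terms and any subject term, and each attribute effect it targets is a single pairwise product contrast labelled as marginal.

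*SAP*

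**What the plan says.** SAP 7.3 plans a multivariate analysis "to analyze the marginal effect of nicotine concentration, pH and moisture of NP 1.0 products", and states: "This analysis will be done using only NP 1.0 data". Each attribute is coded low or high. The model line is "model log(PK parameter) = Nicotine_concentration PH Moisture/ddfm=KR solution", run under a BY statement on product, with no RANDOM or REPEATED statement. The listed outputs are the percentage of variance explained and a standardized effect, the latter being the mean effect over the square root of its variance. No confidence intervals are listed.

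Protocol 12.6.2.3 describes this analysis as one of joint effect. On adjustment it says: "The model will include be adjusted for product use, sequence, period", followed by the three coded attributes. Its outputs are regression coefficients with confidence intervals.

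SAP 9 lists two changes, neither concerning this model, and closes: "All other analyses described in this SAP are aligned with those analyses described in the protocol".

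The main PK model in SAP 6.5.1 has sequence, period and product effects and a within-subject covariance structure. Its Table 6.2 already includes every pairwise comparison among the four NP 1.0 variants.

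**The concern.** Two things look wrong, and both remain after the BY statement is corrected.

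First, the model ignores the crossover. Every subject is planned to use all four variants, so attribute effects are within-subject comparisons. With no subject term, between-subject variance goes into the residual. Dropping sequence and period also departs from the protocol without being declared.

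Second, the label promises more than four products can deliver. pH varies only among the 8.4 mg pouches, and moisture only among the 3.6 mg pouches. A pH effect reported as marginal could be read as applying at 3.6 mg, where it was never observed.

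At stake are the protocol's confidence intervals, the SAP's two output measures, and the possibility of two differing intervals for the same product contrast in one report.

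**Working it through.** **Inputs.** From protocol 12.9.5: n = 24, GCV of Cmax 40% for all products, within-subject correlation 0.7 on the log scale, precision target 15% or less. From the protocol synopsis: true ratio 1. Attribute levels come from protocol 6.1 and SAP Table 5.1.

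**1. The plan's own precision figure.** Log-scale SD = sqrt(ln(1 + 0.40²)) = sqrt(0.1484) = 0.385. Paired SE = 0.385 × sqrt(2 × (1 − 0.7)/24) = 0.0609.
- With t on 110 df (six-product crossover ANOVA: 144 records − 24 subjects − 5 product − 5 period terms), the half-width is 0.121, or +12.8%/−11.4%.
- With a paired t on 23 df, it is 0.126, or +13.4%/−11.8%.

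Both are within 15%. A simulation of 10,000 Williams crossovers gave mean precision 12.8%, 99% of runs within 15%, and coverage 94.9%. The protocol states only an upper bound, so the check confirms the bound and not a point value.

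**2. The code as printed.** Within one product, nicotine, pH and moisture are constant. The design matrix (intercept plus three attributes) has rank 1 in each of the four products. No attribute effect is estimable.

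**3. BY removed, nothing added.** There are 24 × 4 = 96 records and four parameters, leaving 92 residual df. SE = 0.385 × sqrt(2/24) = 0.1112. Half-width = 1.986 × 0.1112 = 0.221, or +24.7%/−19.8%.
- SE ratio: 0.1112/0.0609 = 1/sqrt(1 − 0.7) = 1.83.
- Half-width ratio: 0.221/0.121 = 1.83 against the 110-df interval, and 0.221/0.126 = 1.75 against the 23-df interval. Simulation gave 1.82.
- In simulation the nominal 95% interval covered about 99.9% and met 15% precision in about 0.01% of runs. About 59 subjects would be needed for 15% without pairing.

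Sensitivity of the SE ratio to the assumed correlation:

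| Correlation | 0.5 | 0.6 | 0.7 | 0.8 |
|---|---|---|---|---|
| SE ratio | 1.41 | 1.58 | 1.83 | 2.24 |

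**4. Effect on the SAP's outputs.** At correlation 0.7, the residual variance of 0.148 contains 0.7 × 0.148 = 0.104 of between-subject variance, which dilutes the percentage explained. If the variance in the standardized effect means sampling variance, that measure is multiplied by 1/1.83 = 0.55.

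**5. What the coefficients are.** Coding high as 1 and low as 0:

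| Product | Intercept | Nicotine | pH | Moisture |
|---|---|---|---|---|
| NP-1 | 1 | 1 | 0 | 1 |
| NP-2 | 1 | 1 | 1 | 1 |
| NP-3 | 1 | 0 | 0 | 0 |
| NP-4 | 1 | 0 | 0 | 1 |

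The matrix has rank 4, so four parameters reproduce four product means exactly. Inverting it gives, on the log scale:
- nicotine = NP-1 − NP-4 (at pH 8.0, moisture 30)
- pH = NP-2 − NP-1 (at 8.4 mg, moisture 30)
- moisture = NP-4 − NP-3 (at 3.6 mg, pH 8.0)

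No degree of freedom is left for an interaction. If the protocol's adjustment for product use means product, the attributes are fully aliased with it.

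**The case against.** The strongest reply is that the 1.8-fold factor is not a property of the printed analysis. That is correct. A reader might infer that SAP 7.3 as written yields over-wide intervals. It yields no attribute estimate at all, and it lists no intervals (its model options request none). The factor describes the code after the obvious repair of deleting BY, and the intervals it affects are those promised in the protocol.

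A reader might also infer that the product comparisons are compromised. They are not. All three contrasts appear with 95% CIs in the main model, the study is exploratory with no pre-specified hypothesis, and losing the pairing errs on the conservative side.

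The label can be defended, since a coefficient from a main-effects model is marginal if effects add on the log scale. It would also go too far to say that no joint effect can be estimated: once BY is removed, the three attributes can be fitted and tested together. Only interaction is out of reach. Neither document draws a pH conclusion for 3.6 mg pouches.

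Finally, SAP 7.3 describes a further ANCOVA with a random subject effect. This does not clearly supply the missing term: its code models a PD score, and protocol 12.6.2.3 places that ANCOVA with the PK-PD analysis.

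What stands after these replies is the undeclared loss of sequence and period, the absent subject term, and a label that depends on an unstated assumption.

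**Conclusion.** The point holds as a defect of specification and labelling in a supplementary analysis. The SAP model omits sequence and period contrary to the protocol, has no within-subject term, and SAP 9 does not say so. Deleting BY alone would give code that runs but ignores the crossover, with standard errors about 1.8 times the paired ones. That size rests on the protocol's Cmax assumptions. Neither the GCV nor the correlation is stated for AUCs, so the factor may differ there.

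Point estimates would be unchanged only with complete balanced data. Protocol 12.6.2 sets non-adherent periods to missing and relies on model-based REML under MAR. A model without subject or period cannot use a subject's remaining periods, so its ratios could then differ from those of the main model.

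The identification of each attribute effect with one pairwise contrast is exact and needs no assumption about variability.

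**What to change.** Choose one of two repairs.

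1. **Keep the model.** Remove the BY statement and add sequence, period and a within-subject term (random subject, or the repeated structure of SAP 6.5.1). Do not add a product term, because product determines the attributes. State whether the variance in the standardized effect is sampling variance, and restore the protocol's coefficients with confidence intervals.
2. **Replace the model.** Report NP-1/NP-4, NP-2/NP-1 and NP-4/NP-3 from the SAP 6.5.1 model with 95% CIs. This gives up the variance-explained output. It keeps the pairing as long as 6.5.1 converges with its planned covariance structure.

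In both cases, describe each effect as conditional on the levels at which the other attributes are held, state that interaction cannot be assessed, and record the departure from protocol 12.6.2.3 in SAP 9. The cost is SAP wording, a few lines of code and the matching table shells. No change to data collection is needed.

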12.1.1 Stratification Criteria

The sample enrollment will enforce at least 25% of each sex, therefore demographics, baseline characteristics, PK and PD parameters analyses will be stratified by sex, as well as unstratified, as detailed in the SAP.

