3.1 STUDY DESIGN

This is a single-center, randomized, controlled, open-label, cross-over study in healthy smoking subjects to investigate the nicotine PK profiles of 4 variants of NP 1.0 compared to marketed Velo-NP and Zyn-NP. In addition, PD effects will be evaluated to provide further insights on NP 1.0 product acceptance and abuse liability. The study will be conducted with 6 product use periods and 6 sequences in a Williams design (cross-over).

A Screening Visit will be conducted within 21 days (Day -22 to Day -2) prior to Admission (Day -1) to the investigational site (Figure 1). Subjects will be screened against eligibility criteria.

Statistical Analysis Plan Number CA36095

Figure 1 Study Design

Qualified subjects will return to the investigational site for Day -1. Subjects should have fasted for at least 10 hours prior to the safety laboratory assessments. After confirmation of eligibility, subjects will be enrolled. All subjects that are not enrolled will be considered as screen failures.

On Day -1, enrolled subjects will perform a product test using NP-1 for 30 minutes (\pm 1 minute). After the product test, subjects not willing and/or not ready to use NP 1.0 during the study will be discontinued from the study, will enter the 3-day Safety follow-up period, and will be replaced.

Subjects willing and ready to use NP 1.0, Velo-NP and Zyn-NP during the study after product test will start their exposure period of 3 days.

Twenty-four (24) subjects will be randomized to 1 of 6 possible sequences of product use on Day 1 to Day 3 with at least 25% of each sex (see Figure 1). The randomization process including the randomization sequences will be documented in the randomization plan.

On Day 1 to Day 3, after at least 8 hours of abstinence from any nicotine/tobacco containing products (nicotine wash-out), subjects will use one NP for 30 minutes (± 1 minute) according to randomized product use sequence in the morning and in the afternoon, by placing the NP between the upper lip and gum. Subjects will complete self-reported assessments of product evaluation, craving, liking, satisfaction, and intent to use again.

The start of the 30 minutes use period will be defined as T₀. T₀ in the morning (T_{0M}) and in the afternoon (T_{0A}) on Day 1 to Day 3 should be approximately at the same time, within a window of \pm 30 minutes. Venous blood samples will be obtained according to the standard operating procedures (SOPs) at the investigational site.

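### SAP 7.3: the PK-PD ANCOVA described as overall is coded by product and sex, so it gives no pooled slope and cannot separate subject variance

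*SAP*

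**What the plan says.** SAP 7.3 sets out two PK-PD analyses for Objective 4. Of the first it says: "An analysis of covariance (ANCOVA) will be conducted by product use". The second is introduced as the same apart from one exception: "it will be performed overall using mixed effects ANCOVA where the model will include, in addition, the subject as a categorical random effect". The stated purpose of the random effect is to model correlation within subjects. Protocol 12.6.2.3 specifies the same second analysis: "it will be performed overall using mixed effects ANCOVA where the model will include additionally the subject as a categorical random effect".

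The SAP then gives the code with which this second analysis is to be run: "By product sex; class subject sequence period; model log(PK parameter) = sequence period score/ddfm=KR solution; random subject; run". Product appears only in the BY statement, not in the CLASS or MODEL statement.

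On sex, protocol 12.1.1 says that "PK and PD parameters analyses will be stratified by sex, as well as unstratified". SAP section 9 lists the departures from the protocol, does not mention this one, and closes with "All other analyses described in this SAP are aligned with those analyses described in the protocol".

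**The concern.** The text and the code describe different analyses. Since the second ANCOVA is contrasted with one done by product, overall can only mean not split by product. The code keeps the split by product and adds a split by sex.

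Two things are then lost. A random subject effect needs at least two records per subject in the same fit, and here there is only one. A slope relating PK to the subjective scores across products needs all products in one fit, and here each fit sees one. Among the PK-PD analyses, this is the only one meant to combine a subject's six product uses.

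**Working it through.** The plan states no figure for this analysis, so there is none to reproduce. Its sample-size statement concerns the precision of a Cmax ratio and does not bear on the point.

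**Inputs**
- 24 subjects, 6 sequences, 6 product-use periods, Williams design (SAP 3.1). Each subject uses each of the six products once.
- Each averaged VAS score is one value per subject per product use (SAP 7.1.2 to 7.1.4); PES and the sensory questionnaire are completed once per product use (SAP 7.1.1, 7.1.6).
- At least 25% of each sex (SAP 3.2), so 6 to 18 subjects of either sex.
- Assumed: complete data and 4 subjects per sequence. The randomization list is not in the documents.

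**Step 1: number of fits.** 6 products × 2 sexes = 12 fits per PK-PD pair. Objective 4 lists these pairs: liking 2 averages × 3 PK parameters = 6; satisfaction 3; craving 3; PES 7 scales × 1 = 7; sensory 9 items × 1 = 9. The total is 28, and 28 × 12 = 336 group slopes with no pooled slope. Counting only the four multi-item PES subscales gives 25 pairs and 300 slopes.

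**Step 2: records per subject.** One product and one sex leave at most one record per subject. With Z the subject design matrix, ZZ′ = I, so the covariance is V = σ²(subject)·I + σ²(residual)·I, and the two variances enter only as their sum. As a numerical check, simulated data for 12 subjects of one sex, with total variance ln(1 + 0.40²) = 0.1484 from the 40% geometric CV in protocol 12.9.5, gave the same REML log-likelihood (−2.17897773) whether the subject share was 0, 0.3, 0.7 or 0.95. Removing only sex from the BY statement does not help: 24 records from 24 subjects is still one each.

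**Step 3: what each group fit has left.** Ignoring the random term, the fixed part is sequence, period and score. Within one product each sequence corresponds to exactly one period, so period adds nothing beyond sequence. With n subjects spread over k sequences, rank = min(n, k + 1) and residual df = n − rank.

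| Group | Residual df, fixed effects only |
|---|---|
| 6 subjects, k = 6 | 0, slope not estimable |
| 6 subjects, k = 5 | 0 |
| 6 subjects, k = 4 | 1 |
| 7 subjects, k = 6 | 0 |
| 8 subjects, k = 6 | 1 |
| 12 subjects | at least 5 |
| 18 subjects | at least 11 |
| 24 subjects (by product only) | 17 |

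All six product groups of a given sex share the same value.

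**Step 4: how likely the poor cases are.** Suppose the minority sex has 6 subjects placed at random among the 24 sequence slots, which gives C(24,6) = 134,596 placements.
- k = 6: 4⁶ = 4,096 (3.0%).
- k = 5: 6 × 5 × 6 × 4⁴ = 46,080 (34.2%).
- k = 4: 15 × (1,024 + 3,456) = 67,200 (49.9%).
- k ≤ 3: the remaining 17,220 (12.8%).

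So 0 df has probability (4,096 + 46,080)/134,596 = 37.3%. With 7 subjects it is 36,864/346,104 = 10.7%; with 8 or more it is nil. If sex were instead balanced over sequences, 6 subjects would always give a slope that cannot be estimated, 7 would always give 0 df, and 8 would give 1.

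**Step 5: the pooled model.** 24 × 6 = 144 records. Fixed rank is 1 + 5 (sequence) + 5 (period) + 1 (score) = 12; subject within sequence takes 23 − 5 = 18; residual df = 144 − 12 − 18 = 114. Adding product costs 5 more, leaving 109. With six records per subject the two variances separate.

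**The case against.** The intention is plain and stated in both documents, and the likeliest cause is a BY line carried over from the by-product code just above. A programmer comparing text and code would see the conflict. The analysis is supplementary, in a study with no hypothesis and no multiplicity control. This limits the importance of the point. It does not remove it: the SAP presents this as the code to be used, and correcting it at the analysis stage would also mean deciding, with data in hand, whether product is in the model.

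The sex split might be the stratified run foreseen in protocol 12.1.1. That section asks for unstratified results as well, and it does not explain the split by product.

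The percentages in Step 4 depend on random placement of the sexes. SAP 3.2 calls the population stratified by sex, and SAP Table 4.1 refers to misclassified sex at randomization, so sex may be a randomization stratum; protocol 12.9.1 mentions only a quota. The objection stands to this extent: the percentages are one scenario. Under balance, the result at the 25% floor is worse.

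Finally, inseparable variances do not make every group slope inestimable; the slope can be estimated wherever the fixed-effect design allows. That is correct. What PROC MIXED would report for the confounded variance was not tested.

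**Conclusion.** The concern holds and should be fixed before analysis. As printed, the code yields 12 product-by-sex slopes per PK-PD pair and no pooled slope, and the random subject effect cannot do its stated job. These conclusions rest only on each subject using each product once. They are unchanged whether period is read as six product uses (SAP 3.1, protocol 12.9.1) or three periods (protocol synopsis and 4.1).

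The degrees-of-freedom figures also assume complete data and 4 subjects per sequence; the pooled figures take six periods, and the percentages assume random placement of the sexes. The loss is confined to the pooled part of Objective 4. The by-product ANCOVA and the main PK comparisons in SAP 6.5.1 stand.

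**What to change.** Delete the BY statement from the code for the overall model, so that all six uses per subject are fitted together with random subject. Leave Tmax unlogged, as the text of SAP 7.3 already requires.

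State in the SAP whether product is a fixed effect; the terms listed in protocol 12.6.2.3 do not include it. With product in the model, the slope is adjusted for differences between products. Without it, those differences enter the slope. Reporting both is reasonable. Any run by sex should be additional to the unstratified one.

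The cost is one line of SAS code and one sentence in the SAP before analysis. Nothing in study conduct changes.
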